4.2 Exclusion Criteria

A subject will not be eligible for inclusion in this study if any of the following criteria apply:

1. Subject is receiving concomitant treatment with voxelotor, crizanlizumab, or L-glutamine.
2. Subject has any history of stem cell transplant is planning to begin or has received in the past 30 days.
3. Subject experiences an acute VOC, requiring a visit to a medical facility and/or healthcare professional, ending within 7 days prior to Day 1 dosing.
4. Subject has received any blood products within 30 days of Day 1 dosing.
5. Subject has uncontrolled liver disease or renal impairment, ulcerative colitis, Crohn's disease, or other chronic GI disorder.
6. Subject has received active treatment in another investigational trial within 30 days or 5 half-lives of the last dose of the investigational agent, whichever is greater, prior to Screening.
7. Subject has received penicillin prophylaxis or antibiotics for treatment of infection within 30 days or 5 half-lives of the treatment, whichever is greater, prior to Screening.
8. Subject has a significant medical condition that required hospitalization (other than for a VOC) within 2 months prior to Screening.
9. Subject is planning on undergoing an exchange transfusion during the duration of the study or has completed one within 4 weeks prior to Day 1 dosing.
10. Subject has a hypersensitivity to rifaximin, rifampin, rifamycin antimicrobial agents, or any components of rifaximin ER and DER.
11. Subject is pregnant or a nursing woman.
12. Subject has a history of illicit drug use or abuse, either documented or in the opinion of the Investigator.
13. Subject is using any medication that is known to inhibit or induce CYP3A4, P-gp, or OATP1B1/B3 (See Appendix 3) within 30 days or 5 half-lives, whichever is longer, prior to Day 1 dosing, or in the opinion of the Investigator, may affect the evaluation of the study product or place the subject at undue risk.
14. Subject has had any prior gastrointestinal surgery which has altered the anatomy of the esophagus, stomach, or small/large intestine (with the exception of appendectomy, cholecystectomy, and fundoplication).
15. Subject has had a colonoscopy or sigmoidoscopy within 30 days prior to Day 1 or plans to undergo such a procedure during the duration of the study.

16. Subject has used bowel prep, laxative, or enema within 30 days prior to Day 1.
17. Subject has a bleeding disorder including, but not limited to, acquired or congenital platelet function defects, disseminated intravascular coagulation (DIC), bleeding factor deficiencies, hemophilia, idiopathic thrombocytopenia purpura (ITP), or von Willebrand's disease.
18. Subject is planning to undergo a major surgical procedure during the duration of the study.
19. Subject has a positive test for human immunodeficiency virus (HIV)1 or HIV2.
20. Subject has an active Hepatitis B infection (HBsAg positive). Prior infection that is not active (i.e., HBsAg negative, HBcAb positive, and HBsAb positive) is permitted.
21. Subject has a positive test for Hepatitis C (HCV RNA). Prior infection with spontaneous resolution or sustained resolution for ≥ 24 weeks after cessation of antivirals is permitted.
22. Subject has an active COVID-19 infection or complication(s) related to COVID-19 infection that are unresolved or, in the opinion of the Investigator, may affect evaluation of the study drug or place the subject at undue risk.
23. Subjects has received a vaccine (including COVID-19 vaccine) within 2 weeks prior to Screening. If subject has received their first of two COVID-19 vaccination doses, as applicable, they must wait for at least 2 weeks after receiving the second dose, and be symptom-free, prior to beginning Screening. Subject must not be planning for COVID-19 or other vaccinations while on study.
24. Subject has a malignant disease. Exceptions include malignancies that were treated curatively and have not recurred within 2 years prior to study treatment, completely resected basal cell and squamous cell skin cancers, and any completely resected carcinoma in situ.
25. Subjects has prolonged QT interval as assessed by ECG history within the past 3 months. For subjects with no historical ECG information, subject has a resting QTcF ≥ 460 msec for males and ≥ 470 msec for females at Screening.
26. Subject has any unstable cardiac condition that, in the opinion of the Investigator, may worsen during the study or interfere with successful evaluation of the study treatment.
27. Subject has a serious mental or physical illness which, in the opinion of the Investigator, would compromise participation in the study.
28. Subject has any condition which, in the opinion of the Investigator, is likely to interfere with the successful collection of the measurements required for the study.
29. Subject is unable to understand or comply with study instructions and requirements.

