4.3 Concomitant Therapies

A concomitant medication is any drug or substance administered between the signing of the informed consent and the EOS/ET Visit. The use of concomitant therapies or procedures must be recorded on the subject's eCRF, according to instructions for eCRF completion. Adverse events related to administration of these therapies or procedures must be documented in the appropriate eCRF.

Other than the medications listed in Section 4.3.1, medications that are used as the standard of care for SCD will be allowed during the study.

Use of HU/HC is allowed during the study. However, subjects receiving should maintain a stable dose throughout the study.

A COVID-19 vaccination is to be recorded as concomitant medication.

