4.3.1 Prohibited Medications and Therapies

Treatment with the following is not allowed during the study:

- Non-study rifaximin (e.g., commercial rifaximin, XIFAXAN® 550 mg tablets), rifampin or other rifamycin derivatives are prohibited within 30 days of providing consent, and throughout the study.
- Initiation of treatment with HU/HC, voxelotor, crizanlizumab, or L-glutamine.
- COVID-19 vaccination.
- Gene therapy for SCD.
- Initiation of a chronic transfusion program (pre-planned series of transfusions for prophylactic purposes).
- Enrollment in any other drug, biologic, or device clinical study or treatment with an approved therapy for investigational development or unapproved investigational drug under development is not allowed.
- Chronic antibiotic use throughout the study is prohibited. A short-course of antibiotic therapy (\leq 7 days; non-rifamycin and non-quinolone classes only) to treat infections such as sinusitis, urinary tract infections, etc. or for dental therapy prophylaxis is permitted. Longer courses of therapy will require the permission of the Sponsor.
- Treatment with CYP3A4 inhibitors/inducers, P-glycoprotein (P-gp) inhibitors/inducers, and organic anion transporting polypeptide (OATP1B1/B3) inhibitors shown in [Appendix 3](#).
- Use of proton pump inhibitors (PPIs).

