6.1 Study Schedule by Treatment Visit

6.1.1 Visit 1; Screening (Day -21 to Day -1)

The initial Screening Visit (Visit 1) should be conducted between Days -21 and -1, inclusive. The following procedures are to be completed at Visit 1:

- Obtain informed Consent signed by the subject prior to performing any study evaluations or procedures including asking subjects to discontinue any prohibited medications.
- Record demographics and medical history information. Detailed history of VOCs occurring over the past 12 months will be obtained. This will include collection of treatments for VOCs including drug, dose, route of administration, duration of treatment, and inpatient/outpatient setting.
- Record all opioid use within the 30 days prior to Screening.
- Review Inclusion/Exclusion criteria to ensure subject qualifies for the study.
- Obtain height and weight.
- Obtain vital sign measurements. Vital signs to be collected are blood pressure (BP) heart rate (HR), body temperature, and O₂ saturation.
- Conduct full physical examination.
- Obtain electrocardiogram (ECG; 12-lead).

- Collect blood samples for hematology, blood chemistry, coagulation, and viral testing, and urine sample for urinalysis.
- Perform hemoglobin genotyping (for subjects with unknown genotype).
- Conduct serum pregnancy test for women of childbearing potential (WOCBP).
- Record concomitant medications (record all medications within 30 days of Visit 1).
- Have subjects discontinue use of prohibited medications immediately after Visit 1 (Screening).
- Record adverse events.
- Schedule Visit 2 (Day 1).

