6.1.2 Visit 2; Randomization (Day 1)

Randomization will be performed on Day 1. Participants will be in a fasted state. There is no Day 0 in this protocol. The following assessments are to be completed prior to randomization:

- Review Inclusion/Exclusion Review to ensure subject continues to qualify for the study.
- Collect any adverse events since the Screening Visit.
- Collect concomitant medication changes since the Screening Visit. Specifically collect opioid use since Screening.
- Obtain vital sign measurements (BP, HR, body temperature, and O₂ saturation.)
- Conduct symptom-directed physical exam, as needed.
- Obtain ECG (12-lead).
- Collect blood samples for hematology and blood chemistry and urine for urinalysis.
- Collect blood samples for CANs, CD62L, iFABP and LPS.
- Collect urine sample for 3-indoxyl sulfate.
- Confirm negative serum pregnancy test from Screening and conduct urine pregnancy test for WOCBP.
- Query subject and record VOCs that have occurred since Screening.
- If subject continues to meet eligibility requirement, randomize subject.

After randomization, conduct the following assessments:

- Collect pre-dose PK sample.

- Dispense study drug and instruct subject in administration (i.e., number of capsules to take [2 or 4] and timing of BID dosing).
- Have subject administer first dose of study drug.
- Collect PK blood samples at 0.5, 1, 1.5, 2, 3, 4, 5, and 8-hours post-dose.
- Record any concomitant medications.
- Record any adverse events.
- Schedule Visit 3

6.1.3 Visit 3, (Day 8 ±1 day) and Visit 4, (Day 15 ±1 day)

Participants will be in a fasted state. The following assessments are to be completed at Visit 3 and Visit 4:

- Collect any adverse events since Visit 2 or Visit 3.
- Collect concomitant medication changes since Visit 2 or Visit 3. Specifically collect opioid use since Visit 2 or Visit 3.
- Obtain vital sign measurements (BP, HR, body temperature, and O₂ saturation.)
- Conduct symptom-directed physical exam, as needed.
- Collect blood samples for hematology and blood chemistry and urine for urinalysis.
- Collect blood samples for CANs, CD62L, iFABP and LPS.
- Collect urine sample for 3-indoxyl sulfate.
- Query subject and record VOCs that have occurred since Visit 2 or Visit 3.
- Collect unused study drug and review compliance and accountability.
- Collect pre-dose PK sample.

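### Exclusion 7 counts the antibiotic washout back from Screening, not Day 1, so some short courses can end the day before the baseline PD sample

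*Combined protocol and SAP*

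**What the plan says.** Section 4.2, Exclusion 7, bars penicillin prophylaxis or "antibiotics for treatment of infection within 30 days or 5 half-lives of the treatment, whichever is greater, prior to Screening". The synopsis uses the same anchor. Section 6.1.1 sets the distance from Screening to Day 1: "The initial Screening Visit (Visit 1) should be conducted between Days -21 and -1, inclusive".

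Section 4.3.1 bars chronic antibiotic use but tolerates courses of up to 7 days: "non-rifamycin and non-quinolone classes only) to treat infections such as sinusitis, urinary tract infections, etc. or for dental therapy prophylaxis is permitted". Section 4.3 starts the concomitant-medication period at consent: "A concomitant medication is any drug or substance administered between the signing of the informed consent and the EOS/ET Visit".

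On Day 1, before randomisation, Section 6.1.2 asks the site to "Review Inclusion/Exclusion Review to ensure subject continues to qualify for the study" and to "Collect concomitant medication changes since the Screening Visit". The baseline PD samples are taken at the same visit, before dosing.

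Other criteria in Section 4.2 use Day 1 as the anchor. Exclusion 3 concerns a VOC "ending within 7 days prior to Day 1 dosing". Exclusion 4 reads "Subject has received any blood products within 30 days of Day 1 dosing". Exclusions 13 (interacting drugs), 15 (lower endoscopy) and 16 (laxatives, enemas, bowel preparation) also count back from Day 1, as does the completed exchange transfusion in Exclusion 9.

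**The concern.** The washout protects the time before Screening and leaves the time between Screening and the baseline sample open. The Day 1 re-check does not close the gap, because it re-applies a criterion that looks only behind Screening. A laxative taken on Day -10 excludes a subject, while a permitted antibiotic on Day -10 does not.

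The order of strictness sits badly with the protocol's own reasoning. Section 1.2 cites mouse experiments in which broad-spectrum antibiotics depleted the gut microbiota and reduced aged neutrophils. Circulating aged neutrophils (CANs), gut-permeability markers and a gut-bacteria marker are all PD measures here. PK/PD is a stated objective, and Section 8.4.5 summarises PD as change from Baseline, so one disturbed baseline carries into every later change value for that subject.

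**Working it through.** **Inputs**
- Washout of 30 days, or five half-lives if longer, counted back from Screening (Section 4.2, Exclusion 7).
- Screening on any day from -21 to -1 (Section 6.1.1). There is no Day 0 (Section 6.1.2), so Day -s is s days before Day 1.
- Tolerated course of at most 7 days (Section 4.3.1).
- Twelve subjects per active group, and 6 + 6 = 12 in the pooled placebo group (Sections 3.2 and 8.4.1).
- Seven PD markers (ANC, CANs, CD62L, hsCRP, iFABP, LPS, urine 3-indoxyl sulfate) at Days 8, 15, 29, 31 and 43 after baseline (Section 2.2.1).

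The plan states no antibiotic-free interval before Day 1 and no power calculation, so it has no figure of its own to reproduce.

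**1. Antibiotic-free interval before the baseline sample (30-day limb)**
- No course after Screening: at least 30 + s days. Screening on Day -21, -14, -7 or -1 gives 51, 44, 37 or 31 days.
- A 7-day course on Days -7 to -1, which fits if Screening is on Day -7 or earlier: 1 day, which is 29 days short of 30.

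**2. Which antibiotics get through**
- Appendix 3 drugs are caught by Exclusion 13, counted from Day 1. They include azithromycin, clarithromycin, erythromycin, ciprofloxacin and nafcillin.
- Rifamycins and quinolones are barred by Section 4.3.1.
- For other classes, no fixed rule sets an interval before Day 1.

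**3. Does Section 4.3.1 apply during Screening?** It says only that its rules hold during the study. The synopsis counts Screening as part of participation, Section 4.3 starts at consent, and Section 6.1.1 has prohibited drugs stopped straight after Visit 1. All three point to yes. If the answer were no, Exclusion 7 would still not exclude the subject.

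**4. Change values that share the baseline**
- Ceiling, counting each marker once: 7 × 5 = 35.
- Section 6.1.8 and Appendix 1 draw Day 43 hematology and chemistry only for adverse-event follow-up. ANC comes from the hematology differential and hsCRP from the chemistry panel. Without those draws: 5 × 5 + 2 × 4 = 33.

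**5. Weight in a group mean.** If a course shifts one subject's baseline by δ and leaves later values alone, that subject's change shifts by -δ. The mean of 12 shifts by -δ/12, or 8.3% of δ. The documents give no δ for a short course.

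**6. How often (assumption only; the documents give no rate).** Let p be the share of subjects who take such a course between Screening and Day 1. The chance of at least one in a group of 12 is 1 - (1 - p)^12, and the expected number among 60 is 60p.

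| p | At least one of 12 | Expected of 60 |
|---|---|---|
| 2% | 22% | 1.2 |
| 5% | 46% | 3 |
| 10% | 72% | 6 |
| 20% | 93% | 12 |

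**The case against.** The best defence has four parts.

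- **The structure is coherent.** Exclusions govern the time before Screening and concomitant-medication rules take over from consent. Exclusions 6, 8 and 23 also use Screening. That is true, but the criteria closest in kind, on gut, blood and PK confounders, use Day 1.
- **A safeguard exists.** Exclusion 13 lets the Investigator exclude a subject whose medication may affect evaluation of the study product, and eligibility is reviewed again on Day 1. This narrows the gap. It is discretionary and does not name antibiotics, so it does not replace a rule.
- **No effect is shown.** The evidence in Section 1.2 comes from mice given broad-spectrum antibiotics. The human CAN results come from six months of rifaximin, with drops described from 2 weeks, which is longer than a 7-day course. This stands: nothing in the documents shows that a short course of a permitted class moves any of the seven markers in people.
- **Courses during treatment are tolerated too, over a longer period.** Also true. However, a course on treatment touches the samples near it, whereas a disturbed baseline touches every change value. Use after randomisation is a separate question.

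A reader might infer that the active-placebo comparison is biased in favour of one side. The documents do not support that. Exposure precedes randomisation, so it is not tied to treatment, although groups of 12 can be unbalanced by chance. The sign is also open: the antibiotic might lower CANs, while the infection might raise them, since Section 1.1 lists infection as a trigger of VOC and Section 1.2 says CANs may rise during one.

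**Conclusion.** The point holds as a minor but real weakness. For antibiotics outside Appendix 3 and the barred classes, the gap before the baseline sample can be 1 day, against at least 31 to 51 days when nothing is taken after Screening. This rests on the wording of Exclusion 7 and on day counting, and needs no assumption about effect.

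The consequence for the results cannot be sized. Frequency, magnitude and direction are not given, and the effect could be nil. What can be stated is the reach of one affected baseline, calculated above. It would mainly distort within-group change and add noise. The PD summaries are descriptive, the median is among the planned statistics, and affected subjects can be found in the concomitant-medication listings. The protocol keeps all subjects in the PD summaries (Safety Population, Section 8.3) and plans no covariate adjustment (Section 8.5.1). Section 8.0 leaves detailed methods to a separate SAP, so it should not be inferred that a sensitivity analysis has been ruled out.

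**What to change.** Keep the pre-Screening window and extend the Exclusion 7 look-back to Day 1 dosing, in both Section 4.2 and the synopsis. Word the added period to cover antibiotics for treatment or prophylaxis, because the present text names only penicillin prophylaxis while Section 4.3.1 allows dental prophylaxis more generally. Reconcile Section 4.3.1, so that it is clear that a course between Screening and Day 1 affects eligibility or the timing of randomisation. Leave the on-treatment antibiotic rule as it is.

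**Cost.** A text change in three places, with IRB/EC approval of the amendment. Any affected subject would need re-screening, because a fresh 30-day washout is longer than the 21-day Screening window. The documents describe no re-screening procedure, so the amendment should say that it is allowed. If the last dose was on Day -s, the new Screening is at least 30 days after that dose and the new Day 1 at least 31, so the delay is at least 31 - s days. This gives 10 days for s = 21 and 30 days for s = 1, and more where five half-lives exceed 30 days. The number of such subjects is unknown.

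**Optional.** Flag in the listings any PD sample taken near an antibiotic course, using data already collected, and keep the all-data Safety Population summary as the main one.

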	
22. Subject has an active COVID-19 infection or complication(s) related to COVID-19 infection that are unresolved or, in the opinion of the Investigator, may affect evaluation of the study drug or place the subject at undue risk.
 
23. Subjects has received a vaccine (including COVID-19 vaccine) within 2 weeks prior to Screening. If subject has received their first of two COVID-19 vaccination doses, as applicable, they must wait for at least 2 weeks after receiving the second dose, and be symptom-free, prior to beginning Screening. Subject must not be planning for COVID-19 or other vaccinations while on study.
 
24. Subject has a malignant disease. Exceptions include malignancies that were treated curatively and have not recurred within 2 years prior to study treatment, completely resected basal cell and squamous cell skin cancers, and any completely resected carcinoma in situ.
 
25. Subjects has prolonged QT interval as assessed by ECG history within the past 3 months. For subjects with no historical ECG information, subject has a resting QTcF \geq 460 msec for males and \geq 470 msec for females at Screening.
 
26. Subject has any unstable cardiac condition that, in the opinion of the Investigator, may worsen during the study or interfere with successful evaluation of the study treatment.
 
27. Subject has a serious mental or physical illness which, in the opinion of the Investigator, would compromise participation in the study.
 
28. Subject has any condition which, in the opinion of the Investigator, is likely to interfere with the successful collection of the measurements required for the study.
 
29. Subject is unable to understand or comply with study instructions and requirements.

CRITERIA FOR EVALUATION	
Pharmacokinetics and Pharmacodynamics:
 
Full rifaximin and 25-desacetyl rifaximin PK profiles following administration on Days 1 and 29 and truncated profiles on Days 8 and 15 will be evaluated.

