6.2.3.5 Electrocardiogram (ECG)

A 12-lead ECG (Supine) will be performed on all subjects using a standard ECG machine at Visit 1, (Screening), Visit 2 (Baseline), Visit 5 (Day 29/EOT/ET), and Visit 9 (Day 43/EOS), if applicable.

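### Exclusion 25 tests the Screening QTcF only in subjects with no earlier ECG, so a recent normal ECG lets a Screening value at or above its limits pass

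*Combined protocol and SAP*

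**What the plan says.** Exclusion 25 has two parts, worded alike in the synopsis and in section 4.2.

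- **History part, and the opening of the Screening part:** "Subjects has prolonged QT interval as assessed by ECG history within the past 3 months. For subjects with no historical ECG information". The history part states no value in msec and no correction method.
- **Screening part, continued:** "subject has a resting QTcF ≥ 460 msec for males and ≥ 470 msec for females at Screening". Its opening words, quoted above, restrict it.

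The ECG itself is not conditional. Section 6.2.3.5 says it "will be performed on all subjects using a standard ECG machine at Visit 1, (Screening), Visit 2 (Baseline"), and the Screening procedures in 6.1.1 and the schedule in Appendix 1 agree. On Day 1 (section 6.1.2) a further ECG and an eligibility review come before randomization, and the gate is: "If subject continues to meet eligibility requirement, randomize subject".

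**The concern.** The protocol measures QTcF in everyone at Screening but attaches its numeric limits to that measurement only where no earlier ECG exists. Where one does exist, a tracing up to 3 months old settles the matter and the current protocol ECG is not tested. A subject could therefore meet the protocol's own definition of an excluded QTcF at Screening and still be eligible.

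What is at stake is subject safety at entry. After the Day 1 ECG the next scheduled one is on Day 29, and the Day 43 ECG is done only if Day 29 was abnormal (sections 6.1.4, 6.1.8 and 6.2.3.5). The entry check is the main scheduled look at QT before about four weeks of dosing.

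**Working it through.** There is no figure in the plan to reproduce and no arithmetic to do. The check is to read exclusion 25 as a decision rule, list every case, and look for another provision that covers any case left open.

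**Inputs:** exclusion 25 (section 4.2 and synopsis); ECG timing (6.1.1, 6.1.2, 6.2.3.5, Appendix 1); exclusions 26 to 28 (section 4.2); withdrawal rules (4.5).

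**Step 1. The rule, case by case.** The limit means 460 msec for males and 470 msec for females.

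| ECG in past 3 months | QT on that ECG | Screening QTcF | Result under no. 25 |
|---|---|---|---|
| Yes | Prolonged | Any | Excluded, history part |
| Yes | Not prolonged | Below limit | Not excluded |
| Yes | Not prolonged | At or above limit | **Not excluded:** history part not met, Screening part does not apply |
| None at any time | – | At or above limit | Excluded, Screening part |
| None at any time | – | Below limit | Not excluded |
| None, but an older ECG exists | Any | At or above limit | Unclear |

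The third row is the gap. Two subjects with the same Screening QTcF above the limit are treated differently, according only to whether an earlier tracing is on file.

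**Step 2. Could the Screening ECG count as ECG history?** The criterion sets history against a separate value taken at Screening. Since everyone has a Screening ECG, counting it as history would mean that nobody lacked history and the Screening part could never operate. That reading empties half the criterion.

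**Step 3. Does another provision close the gap?** Exclusion 26 needs an unstable cardiac condition, 27 a serious mental or physical illness, and 28 a condition likely to interfere with the study measurements. Each rests on the Investigator's opinion and none contains a QTcF value. The Day 1 review refers back to the same eligibility criteria and adds no limit for the Day 1 ECG. The withdrawal rules in 4.5 are also discretionary.

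**Step 4. Compare with the laboratory criteria.** Inclusion 6 (section 4.1) applies its numeric limits to Screening values in every subject, whatever earlier results exist. Exclusion 25 departs from that pattern and gives no reason.

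**Step 5. The last row of the table.** The condition about missing history may mean none at all, or none within 3 months. On the second meaning the subject is tested at Screening. On the first, neither part applies. The text does not say which is meant.

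**Step 6. The history part.** With no threshold and no correction formula, what counts as prolonged is left to each of about 20 centers in North America, the Middle East and Africa.

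**The case against.** The strongest defence is that no markedly abnormal tracing would go unseen. The Investigator reviews all documented assessments (6.0), repeats the eligibility review with a second ECG on Day 1 (6.1.2), can exclude under nos. 26 to 28, must record clinically significant ECG abnormalities as adverse events (7.2), and can withdraw a subject (4.5). The identical wording in two places may also mean that the two-part rule is deliberate. This stands as far as it goes: enrolling such a subject would take an Investigator who sees the tracing and proceeds. But these safeguards are discretionary and do not supply the numeric test that the criterion itself contains.

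A reader might infer more than the documents support:

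- **That a subject with only an older ECG certainly escapes both parts.** The condition follows directly on the 3-month window and can naturally be read as referring to it. This is an ambiguity, not a demonstrated gap.
- **That a large share of the trial is affected.** Assuming that 40% to 90% of subjects have some earlier ECG gives 0.40 × 60 = 24 to 0.90 × 60 = 54 subjects. The assumption has no source in the documents, includes ECGs of any age, and does not count subjects whose QTcF is actually prolonged.
- **That the ECG summary in 8.4.8 would be compromised.** A pre-dose Day 1 ECG is taken in everyone and abnormal ECGs are listed, so a prolongation present at entry can be recognised. ECG is not among the three safety endpoints listed in 2.2.2, and no planned estimate or test depends on QTcF.
- **That the study drug carries a QT risk, or that the sponsor meant to exclude these subjects.** The documents state neither.

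**Conclusion.** The concern holds as a defect in one eligibility rule. Followed exactly, exclusion 25 does not exclude a subject with a non-prolonged ECG in the past 3 months and a Screening QTcF at or above 460 msec (male) or 470 msec (female). No other provision applies a QTcF value to that subject. The history part is undefined numerically, and its boundary with the Screening part is ambiguous for ECGs older than 3 months.

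The size cannot be given. The affected group is the subjects with both a recent non-prolonged ECG and a Screening value at or above the limit, and the documents provide neither proportion. It may well be small. The conclusion rests only on the wording of the criterion and on the Screening ECG being required of all. Sample size, power and planned analyses are not affected. The change is worth making because it bears on subject safety and is inexpensive.

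**What to change.** In section 4.2 and the synopsis, reconcile exclusion 25 with the Screening ECG required of every subject, so that a normal historical ECG does not take the current one out of the protocol's own QTcF test. Removing the condition that restricts the limits to subjects without historical ECG information would do this without introducing a new threshold.

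The sponsor should also state:

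- how prolonged QT is to be judged on a historical ECG, including the correction method;
- whether lacking historical ECG information means none at all or none within 3 months, if any such condition is kept.

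Which QTcF rule should finally apply, to Screening or to historical tracings, is the sponsor's clinical decision. The cost is about one sentence for the main change, made in two places, plus these two clarifications. It requires no new procedure, because the ECG is already done in everyone. The downside is possibly a few more screen failures.
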